1.0 Objectives

1.1 Study Objectives

The main objective is to compare the test characteristics of the Human Papillomavirus (HPV) self-sampling kit versus clinician-sampled HPV testing for cervical cancer screening. This study seeks to find out if the HPV self-sampling kit is non-inferior to standard clinician-sampling practices.

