1.2 Primary Study Endpoints

The primary outcomes of this study are to analyze the screening results on self-sampling kits compared to clinician-collected HPV test and Pap smear results.

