1.3 Secondary Study Endpoints

Secondary endpoints will include acceptability of self-sampling and barriers to cervical cancer screening. These endpoints will be analyzed to try to circumvent barriers to the cervical cancer screening and ascertain whether self-sampling is a viable alternative.

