2.0 Background

2.1 Scientific Background and Gaps

The American Cancer Society estimates that 4,170 women in the United States (US) will die from cervical cancer in 2018.¹ Screening can reduce cancer mortality by (1) detecting malignancies when they are more treatable² and (2) for some tests, identifying precancerous lesions for removal. Guidelines recommend cytology and/or human papillomavirus (HPV) testing for cervical cancer screening among women ages 30-65 years, but screening rates are suboptimal.^{3,4}

To help bridge these gaps in screening, HPV self-sampling would be an alternative to clinical screening. However, there are concerns about the efficacy and comparability of self-sampling kits as an effective tool to detect cervical cancer.

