2.2 Previous Data

There have been previous studies about the effectiveness of self-collected samples as an alternative to clinician collected samples. Some studies state that HPV testing is more sensitive than Pap testing.⁵ There is a possibility that these two samples have similar sensitivity.⁶ Based on this information, examining test characteristics and acceptability of each technique is necessary to support larger efforts to make self-sampling available.

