7.0 Study Design and Procedures

7.1 Study Design

After identification, a study team member will talk with potential participants over the phone to determine those that meet the study eligibility criteria. HPV self-sampling kits, with the summary explanation of research, will be mailed to study participants to complete within a week.

If a participant is contacted prior to their well-woman appointment: 3-5 days before the well-woman appointment, the research project manager will reach out to check if study participants have completed their HPV self-sampling kit. Those that have completed the kit will complete a survey over the phone and get an appointment reminder. They will mail their HPV self-sampling kit to the Penn State Health clinical lab. Those that have not completed their HPV self-sampling kit will get instructions to not use the HPV self-sampling kit before the well-woman and get an appointment reminder. They will be told they can complete the HPV self-sampling kit one week after their appointment. If the first self-sampling kit is lost or not received, we will mail a second self-sampling kit. They will then go to their appointment where the clinician will perform the Pap smear/HPV test. If the participant did not complete the self-sampling kit, two weeks after the well-woman appointment a study team member will schedule a time to call the participant to determine if she completed the HPV self-sampling kit and, if so, complete a survey over the phone. If the participant is not able to be reached or has not completed the HPV self-sampling kit, the study team will perform up to three follow up calls per participant. Once an HPV self-sampling kit has been completed and the analysis has been received from the Penn State Health Clinical lab, study participants will be mailed their compensation within 1 week. Only one sample per participant will be mailed to the Penn State Health Clinical lab where they will receive and analyze each sample. Analysis of the self-sampling specimens will be conducted to determine HPV DNA positivity to compare to results of the previous Pap/HPV test. In the unlikely event that not enough sample is collected, the participant will still be compensated for their efforts, and the study team will take note of how much sample was deemed too little for analysis and they will be excluded from data analysis. EMR data will be used to check insurance status, and the date and result of PAP/HPV tests

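### Section 1.1 sets out to compare test characteristics for cervical cancer screening, but no disease status is collected, so the data can show agreement with the clinician HPV result and not sensitivity for disease

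*Combined protocol and SAP*

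**What the plan says.** Section 1.1 gives the objective: "The main objective is to compare the test characteristics of the Human Papillomavirus (HPV) self-sampling kit versus clinician-sampled HPV testing", for cervical cancer screening. It adds: "This study seeks to find out if the HPV self-sampling kit is non-inferior to standard clinician-sampling practices". Test characteristics is not defined there or anywhere else. Section 2.2 describes earlier studies in terms of sensitivity and then concludes that "examining test characteristics and acceptability of each technique is necessary to support larger efforts to make self-sampling available".

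The endpoints are narrower than that. Section 1.2 says the primary outcomes are to "analyze the screening results on self-sampling kits compared to clinician-collected HPV test and Pap smear results". Section 1.3 says: "Secondary endpoints will include acceptability of self-sampling and barriers to cervical cancer screening". Section 8.3 describes the primary outcome as concordance or non-inferiority of the two sets of test results, examined with Fisher's exact test and, additionally, Cohen's kappa.

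On data, Section 7.1 has the self-sample tested for HPV DNA positivity and compared with the Pap/HPV result. It then says: "EMR data will be used to check insurance status, and the date and result of PAP/HPV tests". No colposcopy, biopsy, histological grade or cancer diagnosis is listed. Participation lasts up to five weeks (Section 7.3), and identifiers are destroyed once data collection is complete (Section 6.2).

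**The concern.** For a screening test, sensitivity and specificity are defined against the disease being screened for. That is the natural reading of an objective worded as test characteristics for cervical cancer screening, and the background supports it: Section 2.1 says "there are concerns about the efficacy and comparability of self-sampling kits as an effective tool to detect cervical cancer". Estimating either quantity requires each woman's disease status, or a defined reference standard in its place. The plan has neither. The Pap smear does not fill the gap, because Sections 1.2 and 2.1 treat it as a screening test and no section names it as the reference.

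What is at stake is the conclusion. A table showing close agreement could be read, under the objective as worded, as evidence that the kit detects cervical disease as well as a clinician sample does. That depends on whether the discordant women are the ones with disease, which the study does not record.

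**Working it through.** **The plan's own figure.** Section 8.2 gives 197 participants for a significance level of .05 and 0.80 (written as beta, presumably power). It gives no margin, HPV positivity, discordance rate or expected kappa, so 197 cannot be uniquely reproduced. The argument below does not depend on how it was derived; 197 serves only as the table total.

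**Check 1: does an agreement table determine sensitivity?** The cell counts and the number of cases are assumed, since the documents give none.

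| | Clinician positive | Clinician negative |
|---|---|---|
| Self positive | 14 | 2 |
| Self negative | 2 | 179 |

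- Observed agreement = (14 + 179)/197 = 98.0%.
- Chance agreement = (16/197)² + (181/197)² = 0.851.
- Kappa = (0.980 − 0.851)/(1 − 0.851) = 0.86.

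Now suppose two women have disease and place both in one cell. Sensitivity = cases testing positive/2. Specificity = (181 − cases testing negative)/(197 − 2).

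| Cell holding both cases | Sensitivity, self | Sensitivity, clinician | Specificity, self | Specificity, clinician |
|---|---|---|---|---|
| Both positive | 100% | 100% | 181/195 = 92.8% | 92.8% |
| Clinician only | 0% | 100% | 179/195 = 91.8% | 92.8% |
| Self only | 100% | 0% | 92.8% | 91.8% |
| Both negative | 0% | 0% | 91.8% | 91.8% |

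Agreement and kappa are the same in every row. Sensitivity takes any value from 0% to 100%, and even which method is more sensitive is left open. Specificity moves by about one percentage point, because two cases are few against 195 women without disease.

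**Check 2: a less favourable assumed table.** Take 20 clinician-positive women, 17 of them also self-positive, and 4 of the 20 with disease. The 3 women missed by the kit could include from 0 to 3 of the 4 cases. Detection by the kit among clinician-positive cases is then between (4 − 3)/4 = 25% and 4/4 = 100%. This is not full sensitivity, since cases missed by the clinician sample are left out.

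**Check 3: what can be estimated.** Positive percent agreement = both positive/clinician positive. Negative percent agreement = both negative/clinician negative. Exact (Clopper-Pearson) 95% intervals for assumed counts:

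| Measure | Count | Estimate | 95% interval |
|---|---|---|---|
| Positive agreement, about 5% HPV positivity | 9/10 | 90% | 55.5% to 99.7% |
| Positive agreement, about 8% (table in check 1) | 14/16 | 87.5% | 61.7% to 98.4% |
| Positive agreement, about 10% | 18/20 | 90% | 68.3% to 98.8% |
| Positive agreement, about 10% (check 2) | 17/20 | 85% | 62.1% to 96.8% |
| Positive agreement, about 15% | 27/30 | 90% | 73.5% to 97.9% |
| Negative agreement (table in check 1) | 179/181 | 98.9% | 96.1% to 99.9% |

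Positive agreement rests on 10 to 30 women across this range. Overall agreement of 98.0% in check 1 hides the 87.5% among the clinician-positive women.

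**Would adding a disease endpoint help at this size?** At assumed prevalences of high-grade precancer or worse of 0.5%, 1%, 2% and 3%, 197 women give 197 × prevalence = 1.0, 2.0, 3.9 and 5.9 expected cases. With 6 cases all detected, the exact lower 95% limit for sensitivity is still only 54%.

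**The case against.** The strongest reply is that the operative sections already specify agreement. Section 1.2 compares screening results with screening results, Sections 8.2 and 8.3 speak of concordance, and no section names sensitivity, specificity or cervical disease as an endpoint. On that view, test characteristics in 1.1 is a loose label that could cover agreement with the clinician HPV test. This limits the point to a mismatch between the objective and the analysis. It does not remove it: 1.1 states what the study is meant to conclude, it refers to cervical cancer screening, and the label is nowhere defined as agreement.

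Several stronger readings might be inferred and are not supported:

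- That the plan promises to report disease accuracy or to declare the kit non-inferior. Section 1.1 says only that the study seeks to find out, Section 2.1 reports concerns in the field, and Section 11.2 is conditional on similar findings.
- That specificity is as unknown as sensitivity. Neither is point-estimated, but with rare disease specificity is tightly bounded, as check 1 shows. The force of the point lies in sensitivity.
- That agreement is the only thing the data can give. The two positivity rates and their paired difference are also estimable.
- That the Pap comparison should be demoted. Section 1.2 names it as part of the primary outcome, and nothing in this point requires changing that.

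**Conclusion.** The objective in Section 1.1 goes further than the design can conclude. Without disease status, sensitivity for cervical disease is not identified, and no level of concordance can establish non-inferiority in detecting disease. This follows from the data items listed in Section 7.1 and does not depend on any assumed number.

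The sizes do rest on assumptions. Sensitivity of 0% to 100% with specificity of 91.8% to 92.8% holds for one assumed table with two cases, and 25% to 100% detection holds for 4 assumed cases among 20 clinician-positive women. Neither is a forecast. The documents give no HPV positivity, discordance or disease prevalence.

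The study remains informative about agreement of the self-sampled with the clinician-sampled HPV result. This is a recommended change to the stated objective and to the reporting, not a finding that the design fails.

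**What to change.** - **Section 1.1:** restate the objective as agreement of the self-sampled with the clinician-sampled HPV result. State that sensitivity and specificity for cervical disease are not estimated, and that any non-inferiority conclusion concerns HPV detection relative to the clinician sample only.
- **Section 8.3:** add positive and negative percent agreement with the clinician HPV result, each with an exact 95% confidence interval, alongside kappa.
- **If non-inferiority on agreement is to be claimed:** state the measure and the margin in advance, with the reasoning for the margin. The documents supply none, and 197 has not been justified for positive agreement.
- **Section 1.2:** leave the Pap comparison as it is.

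**Cost.** No added procedure, participant or data item. The changes are wording in 1.1 and two estimates in 8.3. The claim becomes narrower, and the positive-agreement interval will probably be wide enough to limit what can be said. Setting a margin, if that route is taken, is a substantive decision and not a wording change.

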1.2 Primary Study Endpoints

The primary outcomes of this study are to analyze the screening results on self-sampling kits compared to clinician-collected HPV test and Pap smear results.

1.3 Secondary Study Endpoints

Secondary endpoints will include acceptability of self-sampling and barriers to cervical cancer screening. These endpoints will be analyzed to try to circumvent barriers to the cervical cancer screening and ascertain whether self-sampling is a viable alternative.

2.0 Background

2.1 Scientific Background and Gaps

The American Cancer Society estimates that 4,170 women in the United States (US) will die from cervical cancer in 2018.¹ Screening can reduce cancer mortality by (1) detecting malignancies when they are more treatable² and (2) for some tests, identifying precancerous lesions for removal. Guidelines recommend cytology and/or human papillomavirus (HPV) testing for cervical cancer screening among women ages 30-65 years, but screening rates are suboptimal.^{3,4}

To help bridge these gaps in screening, HPV self-sampling would be an alternative to clinical screening. However, there are concerns about the efficacy and comparability of self-sampling kits as an effective tool to detect cervical cancer.

2.2 Previous Data

There have been previous studies about the effectiveness of self-collected samples as an alternative to clinician collected samples. Some studies state that HPV testing is more sensitive than Pap testing.⁵ There is a possibility that these two samples have similar sensitivity.⁶ Based on this information, examining test characteristics and acceptability of each technique is necessary to support larger efforts to make self-sampling available.

2.3 Study Rationale

The impact of the proposed project is to compare HPV self-screening results with Pap smear results, clinician-collected HPV test to ultimately improve the uptake of HPV screening. This study will be conducted in a normal risk population.

3.0 Inclusion and Exclusion Criteria

3.1 Inclusion Criteria

1. Ages 30-65 years
2. PSH patient attending a well-woman visit (i.e., receiving an in-office cervical cancer screening) and able to collect the sample within the collection period (14 days before or 21 days after in-office cervical cancer screening).
3. Female
4. Has an intact cervix
5. Speaks, reads or writes well in English

3.2 Exclusion Criteria

1. Pregnancy
2. Cognitively impaired
3. Incarcerated
4. Complete hysterectomy
5. History of cervical treatment for abnormal Pap/HPV test (i.e., cryotherapy, Loop Electrosurgical Excision Procedure (LEEP))

3.3 Early Withdrawal of Subjects

3.3. 1 Criteria for removal from study

If the subjects does not complete the study activities they will be removed from the study. We don't anticipate clinician removal because study procedures are low risk.

3.3. 2 Follow-up for withdrawn subjects

The withdrawal will be documented and the subject will be replaced if the timeline allows

4.0 Recruitment Methods

4.1 Identification of subjects

- A. Subjects will be identified in one of the following ways from participating Penn State Health clinics when they have a scheduled well-woman appointment:

(1) Clinicians on the study team will prospectively review their clinic schedules two weeks in advance and identify patients that could meet eligibility criteria for this study. They will send the contact information for these patients to study team members through a secure message in the Electronic Medical Record.

(2) Another member of the study team will prospectively review clinician schedules two weeks in advance and identify patients that would meet eligibility criteria for this study. Contact information for these patients will be entered directly into the REDCap database.

The REDCap database is used by study team members for participant tracking and data collection purposes. Separate data collection instruments for participant tracking and data collection will be used within the same REDCap project. Once recruitment is finished, the

contact information for individuals who declined participation or did not respond to recruitment attempts will be deleted.

(3) Clinicians will provide general information (via recruitment info cards and study flyers) about the study during the well-woman visit (if the patient was not previously contacted or was scheduled less than two weeks from their appointment). Patients will be advised to contact the study team using the information on the card/flyer if interested in participating. Study flyers will also be displayed publicly in clinic exam rooms.

Clinic staff who are not members of the study team will also be given recruitment materials, including information cards and study flyers. Non-study team members distributing recruitment materials will direct patients to the contact information provided on the information card and flyer.

(4) After a patient's appointment, if the clinician believes the individual could meet eligibility criteria for the study, the clinician will send the contact information for these patients to the study team members through a secure message in the Electronic Medical Record. For this fourth option, patients would not have been presented with the research opportunity during their appointment; clinicians may not have had a recruitment card available to give to their patient or may simply have forgotten to share the study opportunity. This option is only available for patients of IRB-approved study team members.

(5) Subjects will be identified from participating Penn State Health clinics if they are scheduled to receive a cervical cancer screening with a clinician on the study team. A report of potentially-eligible patients will be pulled from the Penn State Health electronic medical records twice per month via population health reports. Prior to their upcoming appointment, the study team will send a letter (study invitation letter) inviting the individual to participate in the study. A copy of the study flyer will also be included in the mailing. Individuals will be advised to contact the study team using the information on the letter if interested in participating. They will also be advised that they can discuss the research opportunity with their clinician at their upcoming appointment.

Before sending letters to their patients, all clinicians on the study team will be asked to provide permission for the study team to contact their patients. Permission will be given for all patients, not for each individual patient.

4.2 Recruitment process

4.2. 1 How potential subjects will be recruited.

197 subjects will be recruited to participate in the protocol. Clinicians will identify participants they think would be eligible for the study and either provide some general information (via the recruitment cards and study flyers) to the participants or provide their contact information to the study team members so that they may contact the participant themselves. Members of the study team (both clinicians and non-clinical staff) will prospectively review clinic schedules in order to help identify potential participants, and clinicians may also identify patients after their scheduled appointment. This will ensure that enrollment numbers are met and that all potentially eligible participants are provided with a recruitment card and/or study flyer by their clinician or contacted directly by a study team member.

4.2. 2 Where potential subjects will be recruited.

Participants will be recruited at their well-women appointment in the clinician's office or over the phone by a study team member.

4.2. 3 When potential subjects will be recruited.

Potential subjects will be recruited by a clinician at participating clinics when they have a well-woman appointment or are making a well-woman appointment. Participants whose contact information was provided to study team members by the clinician or collected by another member of the study team will be contacted 10-14 days prior to their well-woman appointment. Participants who are given a recruitment card and/or study flyer will contact the study team if they are interested in participating. Participants who are contacted by the study team after their appointment will be contacted within 1-2 days of receiving their contact information from the clinician via the EMR.

4.2. 4 Describe the eligibility screening process and indicate whether the screening process will occur before or after obtaining informed consent. Screening begins when the investigator obtains information about or from a prospective participant in order to determine their eligibility. In some studies, these procedures may not take place unless HIPAA Authorization is obtained OR a waiver of HIPAA Authorization when applicable for the screening procedures is approved by the IRB. [For FDA regulated studies, consent for any screening activities would need to be obtained prior to screening unless specifically waived by the IRB.]

Initial screening will occur before obtaining informed consent via their clinician/other study team member based on patients that are scheduled for upcoming appointments and that likely meet the inclusion criteria, or patients that are identified after their appointment and that likely meet the inclusion criteria. The clinician will then provide a study team member with the phone number of the potential participant, or this information will be entered directly into the REDCap database by a member of the study team. Also, at the well-woman appointment, the clinician may mention the study and give the subject a recruitment card with a study team member's contact information if they are interested. A study team member will complete the screening process and then obtain verbal implied consent over the phone. Then, a study team member will mail the participant the study materials and the summary explanation of research.

